8.5 Special Toxicity Considerations for EVE

8.5.1 Hyperlipidemia

Hyperlipidemia was reported as a serious adverse reaction. It is a recognized side-effect of rapamycins. Use of lipid-lowering drugs should be associated with dietary recommendations. If blood lipid levels exceed the thresholds identified in eligibility criterion 4.2.13, then fasting blood lipid levels will be assessed. As long as blood lipid levels remain below the thresholds in 4.2.13, monitoring of blood lipid levels can continue with patient in a non-fasting state. However, if at any time blood lipid levels exceed these thresholds, further monitoring of blood lipid levels requires patients to be fasting. Fasting status must be verified when interpreting results. For guidance on management of hyperlipidemia refer to Section 8.6.5.

8.5.2 Hyperglycemia

Hyperglycemia was reported as a serious adverse reaction. Similarly, the fasting state of patients should be verified when interpreting results. For guidance on management of hyperglycemia refer to Section 8.6.5.

8.5.3 Pneumonitis

Pneumonitis is a recognized adverse effect of rapamycins (sirolimus, temsirolimus, and everolimus). Numerous case reports in the literature suggest that rapamycin-associated pneumonitis is relatively unaggressive, limited in extent, and reversible upon drug discontinuation. The term 'pneumonitis' is used here to describe non-infectious, non-malignant infiltration in the lungs which is evident radiologically. More precise diagnosis should follow histocytological examination following lung biopsy, generally during bronchoscopy which may or may not be symptomatic. Advice on the management of pneumonitis has been provided in Section 8.6.6.

In oncology studies with EVE, severe pneumonitis suspected as drug-related has been reported as a serious adverse event on 13 occasions and additionally in the following associated preferred terms including acute respiratory distress syndrome (n=2), alveolitis (n=1) and allergic alveolitis (n=1), interstitial lung disease (n=10), lung infiltration (n=23), cryptogenic organizing pneumonia, lung consolidation, pulmonary alveolar haemorrhage, pulmonary toxicity and pulmonary fibrosis (n=1, each). One fatal case of drug-related pneumonitis was reported for a patient with metastatic infiltrating ductal carcinoma of the breast treated with 10 mg/day, which developed approximately two months after starting EVE. Cytology for both the pleural and pericardial fluids was positive for malignancy. The death was considered possibly related to the underlying late stage tumor and study drug. Additionally, one patient treated with 10 mg/day died due to severe acute respiratory distress syndrome and septic shock. Thoracic CT scan demonstrated condensation

in the majority of the left lower lobe and frosted glass appearance in the left upper lobe, lingula, and right lung.

Along with the cases of non-infectious pneumonitis, serious **opportunistic infections** have also been reported in cancer patients treated with EVE: mycobacterium, aspergillus, and fatal candidal sepsis, and fatal pneumocystis carinii in particular. Because EVE, as other rapamycins, inhibits proliferation of activated lymphocytes and reduces neutrophil counts, treatment with EVE must be considered as predisposing patients to the risk of infection. This risk will be higher in patients severely immunocompromised because of their underlying disease and/or co-medications. Outcome may be fatal in case of serious infections.

8.5.4 Myelosuppression

Myelosuppression is frequent when EVE therapy is initiated. Without clinical significance and infrequently, anemia and thrombocytopenia have been reported. In heavily pretreated patients with aggressive lymphoma, the incidence of grade 3 anemia, neutropenia, and thrombocytopenia was reported to be 11%, 16%, and 30%, respectively. Serious, suspected drug-related hemorrhages have been exceptional. Nevertheless, EVE should be considered as predisposing patients to hemorrhage, potentially fatal, should they develop severe drug-related thrombocytopenia.

8.5.5 Liver Function Abnormalities

Discrete, reversible changes in liver enzymes have been found to occur in numerous patients during treatment with EVE in oncology clinical studies, and in a study in rheumatoid arthritis. In oncology studies, these changes may be evident only in patients without severe underlying morbidity. The increase in transaminase's (AST and ALT) generally appears after 4 weeks of treatment. In all but a few cases it does not exceed Grade 1 ($\leq 3.0 \times \text{ULN}$). Similarly, mild increases in alkaline phosphatases can coexist. Spontaneous corrections or intermittent correction with continued treatment can occur. Serum bilirubin is not increased. In studies of patients with advanced cancers, clinically relevant changes in liver enzymes have been invariably associated with the presence of liver metastases and/or progression of the underlying cancer.

8.5.6 Renal Insufficiency

Renal failure has been reported in five suspected cases to date. One patient with no alternative explanation made a complete recovery following study drug adjustment and no treatment/therapy for the event. The rest of the patients had concurrent morbidities, which might have contributed to the reported events.

8.5.7 Hypophosphatemia, hypomagnesemia, hyponatremia and hypocalcemia

These electrolyte abnormalities have been reported as serious adverse reactions. Electrolytes should be monitored in patients treated with EVE.

8.6 Management of Treatment-Related Toxicities

8.6.1 Mucosal Inflammation and Stomatitis:

Stomatitis mostly occurs within the first 8 weeks of treatment. In a single arm study in 92 postmenopausal breast cancer patients, a topical alcohol-free corticosteroid oral solution was administered as a mouthwash during the initial 8 weeks of starting treatment with Afinitor® plus exemestane. In this study, a clinically meaningful reduction in the incidence and severity of stomatitis was observed.

Stomatitis/oral mucositis/mouth ulcers due to EVE should be treated using local supportive care. Please note that investigators in earlier trials have described the oral toxicities associated with EVE as mouth ulcers, rather than mucositis or stomatitis. If your examination reveals mouth ulcers rather than a more general inflammation of the mouth, please classify the adverse event as such. Please follow the paradigm below for treatment of stomatitis/oral mucositis/mouth ulcers:

All patients randomized to EVE should be instructed to do the following, starting one day prior to first dose:

- Maintain good oral hygiene, avoidance of spicy, acidic, hard and hot food and beverages
- Use mild-flavored toothpastes
- Use Alcohol-free steroid-based Mouthwash 10 mL (0.5 mg/5 mL dexamethasone oral solution) swish for 2 mins and spit QID

For mild toxicity (Grade 1), use conservative measures such as **non-alcoholic mouth wash or salt water (0.9%) mouth wash** several times a day until resolution.

For more severe toxicity (Grade 2 in which case patients have pain but are able to maintain adequate oral alimentation, or Grade 3 in which case patients cannot maintain adequate oral alimentation), the suggested treatments are **topical analgesic mouth treatments (i.e., local anesthetics such as benzocaine, butyl aminobenzoate, tetracaine hydrochloride, menthol, or phenol)** with or without **topical corticosteroids**, such as triamcinolone oral paste 0.1% (Kenalog in Orabase®).

Agents containing hydrogen peroxide, iodine, and thyme derivatives may tend to worsen mouth ulcers. It is preferable to avoid these agents. Antifungal agents must be avoided unless a fungal infection is diagnosed. In particular, systemic imidazole antifungal agents (ketoconazole, fluconazole, itraconazole, etc.) should be avoided in all patients due to their strong inhibition of EVE metabolism, thereby leading to higher EVE exposures. Therefore, topical antifungal agents are preferred if an infection is diagnosed. Similarly, antiviral agents such as acyclovir should be avoided unless a viral infection is diagnosed.

Note: Stomatitis/oral mucositis should be appropriately graded using the functional grading given on the NCI-CTC for adverse events, version 4.0.

8.6.2 Rash

For >Grade 1:

- Use fragrance free moisturizing cream or ointment BID over entire body.
- Use ammonium lactate 12% cream or salicylic acid 6% cream BID over dry/scaly/hyperkeratotic areas such as palms and soles.
- Use zinc oxide 13-40% at night for areas with fissures.

For > Grade 2:

- Use topical steroid ointment or cream (Clobetasol 0.05%, Betamethasone 0.05%, Fluocinonide 0.05%) BID and zinc oxide 13-40% at night for areas with fissures.

8.6.3 Nausea/Vomiting

Routine use of prophylactic anti-emetics is NOT recommended.

For Grade \geq 2:

- Begin maximum supportive care and adequate anti-emetic treatments, including ondansetron and aprepitant. May opt to omit if grade I.

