3.5.2 Everolimus Pharmacokinetics (PK)

Everolimus is rapidly absorbed with a median t_{max} of 1-2 hours. The bioavailability of the drug is believed to be 11% or greater. The AUC_{0-T} is dose-proportional over the dose range between 5 and 70 mg in the weekly regimen and 5 and 10 mg in the daily regimen. C_{max} is dose-proportional between 5 and 10 mg for both the weekly and daily regimens. At doses of 20 mg/week and higher, the increase in C_{max} is less than dose-proportional. The coefficient of variation between patients is approximately 50%. Trough levels (24 hour post-dose) correlate well with AUC_{0-T} at steady-state during daily administration. In whole blood, at a daily dose of 10 mg, about 20% of Everolimus is confined in plasma with 26% being unbound. The remaining 80% is sequestered in blood cells.

Everolimus is extensively metabolized in the liver and eliminated in the bile. Major metabolites are inactive. Elimination half-life is approximately 30 hours. The clearance of Everolimus is approximately halved in patients with mild-moderate hepatic impairment (Child-Pugh Class A or B), while renal impairment has little or no impact on the pharmacokinetics of Everolimus.

Age, weight and gender in the adult population do not affect the pharmacokinetics of Everolimus to a clinically relevant extent. The clearance of Everolimus is reduced in children. Pharmacokinetic characteristics are not notably different between Caucasian and Japanese subjects, whereas in Black patients, population pharmacokinetic studies have shown an average 20% higher clearance.

A high-fat meal altered the absorption of Everolimus with 1.3 hour delay in t_{max} , a 60% reduction in C_{max} and a 16% reduction in AUC. Everolimus is a substrate of CYP3A4 and a substrate and a moderate inhibitor of the multi-drug efflux pump P-

glycoprotein (P-gP, MDR1, ABCB1). Hence, its metabolism is sensitive to drugs that modify these enzymes (substrates, inducers, or inhibitors of these enzymes). Competitive inhibition could occur when Everolimus is combined with drugs which are also CYP3A4 or P-glycoprotein substrates. Table 10 (Section 7.3) lists examples of clinically relevant CYP3A inhibitors and inducers. Please refer to Section 7.3 for more information on the concomitant use of CYP3A4 inhibitors/inducers and other medications. More information on Everolimus pharmacokinetics is provided in the [Investigator's Brochure].

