7.2.2 Everolimus

Patients randomized to an EVE-containing arm will receive EVE as a dose of 10 mg orally daily, on a continuous basis. Patients will be instructed to take EVE in the morning, at the same time each day. EVE may be taken with or without food. If vomiting occurs, no attempt should be made to replace the vomited dose. All dosages prescribed and dispensed to the patient and all dose changes during the study must be recorded. EVE will be provided by Novartis Pharmaceuticals Corporation. Antiemetic prophylaxis is not required. However, control of nausea and vomiting may require institution of multiple anti-emetic medication including phenothiazines or 5-HT3 antagonists. Due to its interaction with P450 enzymes, aprepitant use should be avoided.

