7.5 Concomitant Medications

The case report form must capture the concurrent use of all other drugs, over-the-counter medications, or alternative therapies. Patients must adhere to the following:

- Patients will be instructed not to take any additional medications (including over-the-counter products) during the course of the study without prior consultation with the investigator. At each visit, the investigator will ask the patient about any new medications he/she is or has taken after the start of the study drug.
- All Concomitant medications/Significant non-drug therapies taken within 28 days of starting study treatment through the 30- day safety follow up visit, including physical therapy and blood transfusions, should be recorded.
- Patients on chronic medications that can be given concomitantly with the study agents should be continued. The investigator should instruct the patient to notify the study site about any new medications he/she takes after the start of the study drug. All medications (other than study drug) and significant non-drug therapies (including physical therapy and blood transfusions) administered after the patient starts treatment with study drug, and any changes in dosing should be recorded.
- All supportive measures consistent with optimal patient care can be given throughout the study at the discretion of the treating physician, as long as they are not part of the list of prohibited medications. In general, the use of any concomitant medication/therapies deemed necessary for the care of the patient is permitted with the following considerations:
- Prophylactic anti-emetics should be started only once the patient experienced nausea or vomiting at the discretion of the investigator. It is recommended that patients use drugs that do not cause QT prolongation.
- Patients may not receive radiotherapy while on this trial.
- Other investigational therapies must not be used while the patient is on the study

- Anticancer systemic therapy other than the study treatments must not be given to patients while on the study. If such agents are required for a patient then the patient must be discontinued from the study.

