7.6 Drug-Drug Interactions

The following restrictions apply during the entire duration of the study:

- No other investigational therapy should be given to patients.
- No anticancer agents other than the study medication should be given to patients. If such agents are required for a patient then the patient must first be withdrawn from the study.
- Hydroxychloroquine interacts with CYP enzymes, causing potential drug-drug Interations. CYP3A4 modifiers are described below (Table 3) and must be evaluated carefully. Examples are shown in the table. A comprehensive list of cytochrome P450 isoenzymes and CYP3A4 inhibitors, inducers, and substrates can be found at <http://medicine.iupui.edu/flockhart>. This website is continually revised and should be checked frequently for updates.
- Co-administration with strong inhibitors of CYP3A4 (e.g., ketoconazole, itraconazole, ritonavir) or P-glycoprotein (PgP) should be avoided. Seville orange, star fruit, grapefruit and their juices affect P450 and PgP activity. Concomitant use should be avoided
- Co-administration with moderate CYP3A4 inhibitors (e.g., erythromycin, fluconazole) or PgP inhibitors should be used with caution. If patient requires co-administration of moderate CYP3A4 inhibitors or PgP inhibitors, reduce the dose of EVE to 5 mg daily. Additional dose reductions to 5 mg every other day may be required to manage toxicities. If the inhibitor is discontinued the EVE dose should be returned to the dose used prior to initiation of the moderate CYP3A4/PgP inhibitor.
- No chronic treatment with systemic steroids or other immunosuppressive agents (at a dose equivalent of greater than 20 mg prednisone per day) or other immunosuppressive agents) is allowed. Topical or inhaled corticosteroids are allowed.
- For hydroxychloroquine, there are known drug interactions with the following medications: penicillamine, telbivudine, botulinum toxins, digoxin, metoprolol, aurothioglucose, and propafenone. Depending on the specific drug, HCQ increases the levels of these other drugs, or interferes with the activity of the agent (specifically with botulinum toxin) and the combination should be used with caution.

Table 3: Partial List of Prohibited Medications Based on CYP Metabolism

Substrates (competitive inhibition)	
Antibiotics ¹ : clarithromycin* erythromycin	Calcium Channel Blockers: amlodipine diltiazem

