telithromycin* Anti-arrhythmics: quinidine Benzodiazepines: alprazolam diazepam midazolam triazolam Immune Modulators: cyclosporine tacrolimus (FK506) HIV Protease Inhibitors: indinavir* ritonavir* saquinavir* Prokinetic: cisapride Antihistamines: astemizole chlorpheniramine ⁴⁵	felodipine nifedipine nisoldipine nitrendipine verapamil HMG CoA Reductase Inhibitors ² : atorvastatin cerivastatin lovastatin simvastatin Miscellaneous: aprepitant buspirone haloperidol methadone pimozide quinine sildenafil tamoxifen trazodone vincristine
Inducers	
Carbamazepine Phenobarbital Phenytoin* Rifabutin*	Rifampin* St John's wort Troglitazone
Inhibitors	
Amiodarone Cimetidine Clarithromycin Delaviridine Diltiazem Erythromycin Fluvoxamine* Grapefruit juice Sevilla orange	Indinavir Itraconazole* Ketoconazole* Voriconazole* Posaconazole* Mibefradil Nefazodone* Nelfinavir* Troleandomycin Verapamil

Based on: Ingelman-Sundberg M, Human drug metabolising cytochrome P450 enzymes: properties and polymorphisms, Naunyn Schmiedebergs Arch Pharmacol. 2004 Jan;369(1):89-104. and [<http://www.medicine.iupui.edu/flockhart/clinlist.htm> as of July 13, 2006]

* asterisk denotes strong inhibition/ induction

Please note:

strong inhibitor implies that it can cause ≥ 5 -fold increase in AUC or $\geq 80\%$ decrease in clearance of sensitive CYP substrates

moderate inhibitor implies that it can cause 2 to 5-fold increase in AUC values or 50-80% decrease in clearance of sensitive CYP substrates.

(Distinction is not always categorical as interaction can vary according to conditions).

Macrolide antibiotics: Azithromycin is not a CYP3A substrate. It may therefore be employed where antibiotherapy with a macrolide is desirable in a patient being treated with EVE

Statins: Atorvastatin and pravastatin may be associated with EVE, since a PK interaction study has shown that there is no relevant PK interaction.

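### Section 8.6.3 names aprepitant for grade 2 or higher nausea and vomiting, although 7.2.2 says to avoid it and Table 3 lists it as prohibited

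*Protocol*

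**What the plan says.** Protocol 8.6.3 (Nausea/Vomiting) advises against routine prophylaxis. From grade 2 it asks for maximum supportive care and "adequate anti-emetic treatments, including ondansetron and aprepitant". It does not distinguish between arms or study drugs.

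Protocol 7.2.2 (Everolimus) deals with the same clinical situation. It says that controlling nausea and vomiting may need several agents, including "phenothiazines or 5-HT3 antagonists", and then adds: "Due to its interaction with P450 enzymes, aprepitant use should be avoided".

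Protocol 7.6 contains Table 3, titled "Partial List of Prohibited Medications Based on CYP Metabolism". Aprepitant appears there in the block for substrates that compete for the enzyme: "Miscellaneous: aprepitant buspirone haloperidol". Protocol 7.5 leaves supportive measures to the treating physician "as long as they are not part of the list of prohibited medications".

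**The concern.** Staff managing a patient with grade 2 nausea will turn to the toxicity-management section. There they find a named drug tied to a grade, and nothing that sends them back to 7.2.2, 7.5 or Table 3. If they act on it in full, they give a drug that the everolimus section says to avoid.

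The protocol supplies the reason for caution. Section 3.5.2 identifies everolimus as a CYP3A4 substrate and warns: "Competitive inhibition could occur when Everolimus is combined with drugs which are also CYP3A4" or P-glycoprotein substrates. Table 3 places aprepitant in exactly that competitive group. Followed literally, 8.6.3 could add an interacting drug at full everolimus dose in Arms B, C and D, and in Arm A after crossover to the combination. These patients have no overt disease, so an avoidable interaction is hard to justify.

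**Working it through.** No sample size, power or error rate is involved. The check is to compare every mention of aprepitant, together with the rule on supportive drugs.

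| Place in Protocol | Status of aprepitant | Condition or dose rule |
|---|---|---|
| 7.2.2 | To be avoided | Reason given: P450 interaction |
| 7.5 | Excluded if on the prohibited list | General rule for supportive drugs |
| 7.6, Table 3 | On the list, under competing substrates | No exempting note |
| 8.6.3 | Named as treatment from grade 2 | None |

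**Is 8.6.3 a deliberate exception?** Table 3 is not an absolute ban, so this has to be asked. The protocol handles its exceptions openly:

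- Atorvastatin is in Table 3 and is suggested in 8.6.5. A note to Table 3 clears it for use with everolimus and gives a pharmacokinetic reason.
- Erythromycin is in Table 3. Section 7.6 cites it as a moderate CYP3A4 inhibitor, to be used with caution, and says to "reduce the dose of EVE to 5 mg daily".
- Azithromycin is cleared by a note as an alternative macrolide.

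Aprepitant has no clearing note, stated reason or dose rule. Section 8.6.1, in the same part of the protocol, warns against systemic imidazole antifungals because they raise everolimus exposure. Against that background, the wording of 8.6.3 reads as an oversight.

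**Which patients?** Section 7.2.2 concerns everolimus, so its instruction does not reach Arm A during hydroxychloroquine alone. Section 7.6 applies throughout the study and introduces Table 3 through hydroxychloroquine's CYP interactions. Table 3 and 7.5 therefore formally cover those patients too, although the everolimus exposure argument does not.

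**How often could the trigger be met?** The closest data are in the adverse event table in section 3.6, for hydroxychloroquine plus everolimus in renal cell carcinoma (N = 34). It pools grades 1 and 2.

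- Nausea, grade 1–2: 13/34 = 38.2%. Grade 3–4: 0.
- Vomiting, grade 1–2: 4/34 = 11.8%. Grade 3–4: 0.
- Patients with either event: at least 13 (full overlap), or 13/34 = 38.2%; at most 13 + 4 = 17 (no overlap), or 17/34 = 50.0%.
- Patients at grade 2 or higher: at least 0/34 = 0% (every event grade 1); at most 17/34 = 50.0% (every event grade 2, no overlap).

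Section 3.8 describes the same trial with 29 patients and reports two grade 3 episodes of nausea. That is 1/29 = 3.4% if both were in one patient, or 2/29 = 6.9% if in two. The table shows none, and the documents do not explain the difference, so the 0% lower bound holds only for the table.

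These figures describe the combination only. They count patients who might reach the trigger, not patients given aprepitant.

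**The case against.** The strongest reply is that the protocol already settles the matter. Section 7.5 excludes listed drugs from supportive care, 7.6 applies for the whole study, and 7.2.2 names the drug. Against three provisions stands one item in a non-exhaustive list of examples. Someone who reads the whole protocol would choose another anti-emetic, and concomitant medications are reviewed at every cycle. This is largely right, and it limits the seriousness of the point. It does not remove the conflict: 8.6.3 does not refer to the governing rule, and a specific instruction tied to a grade can reasonably be read as overriding a general clause.

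A second reply concerns the dose. The 5 mg rule in 7.6 covers moderate CYP3A4 inhibitors and P-glycoprotein inhibitors, whereas Table 3 lists aprepitant only as a substrate. If it counts as a moderate inhibitor, the rule already applies; if not, no stated rule has been omitted. That is fair, but it also means staff cannot tell from the document which everolimus dose goes with aprepitant.

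Third, the text leading into Table 3 asks only for careful evaluation, which is softer than the table's title. True, but the drug-specific instruction in 7.2.2 does not depend on Table 3.

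Finally, the 0–50% range says little and the exposure change is unknown. Both points stand. The case rests on the contradictory instructions, not on an estimated harm.

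**Conclusion.** The concern holds. In its current operative text, the protocol both advises against aprepitant with everolimus and names it as treatment for a common toxicity, without a written exception. The conflict arises only when staff use the second of the two drugs named in 8.6.3.

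The size of the harm cannot be stated. The documents give no exposure change for everolimus with aprepitant, and only a very wide range for how often the trigger is met. No effect on the feasibility endpoint, toxicity rates or any other analysis is claimed. The conclusion assumes only that 8.6.3 may be read and followed on its own. It should be corrected as a matter of patient safety and consistent conduct across sites.

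**What to change.** Delete aprepitant from 8.6.3 and name the options already allowed in 7.2.2, for example: *start a 5-HT3 antagonist such as ondansetron, or a phenothiazine; avoid aprepitant (see 7.2.2 and Table 3).* Keep the choice subject to the recommendation in 7.5 to prefer drugs that do not prolong the QT interval, and notify sites.

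If the sponsor wants aprepitant as a last resort, 8.6.3 should state the everolimus dose to use with it, and 7.2.2 and Table 3 should carry the exception, as Table 3 does for atorvastatin.

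The preferred change costs a one-line protocol edit and a site notice. Its drawback is one fewer anti-emetic for patients whose nausea or vomiting does not respond to the other agents.
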